#### **10.5 Confidentiality of Patient Data**

The investigator will ensure that the patient's confidentiality is preserved. On eCRFs or any other documents submitted to the Sponsor, the patients will not be identified by their names, but by a unique patient identifier. Documents not intended for submission to the Sponsor, i.e., the confidential patient identification code list, original consent forms, and source records, will be maintained by the investigator in strict confidence.

#### **10.6 Protection of Patient Data**

The investigator, the Sponsor and its representatives will ensure that a potential or actual personal data breach will be immediately (and at the latest within 24 hours of awareness of the incident) notified to the corporate data protection team of the Sponsor (██████████), including a detailed description of the incident. The notification shall be made in accordance with the Sponsor's incident reporting guidance and by using the latest reporting template, indicating the circumstances of the data incident type and amount of personal data involved in the incident. The notification will also report the action

taken to contain or control the incident, estimate the potential harm for the affected individual, and describe the changes that will be implemented to prevent or reduce the risk of a reoccurrence. The Sponsor will investigate all reported incidents to confirm whether a personal data breach has occurred. If a personal data breach is confirmed, the Sponsor will follow the relevant authorized procedure based on the criticality and quantity of the personal data involved.

Potential or actual information security breaches will also be brought immediately (and at the latest within 24 hours of the awareness of the incident) to the attention of the corporate information security team of the Sponsor by using the following e-mail address:

[REDACTED].

## **10.7 Risk Mitigation Plan in Response to the COVID-19 Pandemic**

The Sponsor will continuously monitor and evaluate the development of the COVID-19 pandemic in the areas of study sites to determine if any measures need to be implemented to mitigate undue risks to the subjects or in response to local governmental recommendations. Because patients are required to be on site for administration of the IMP, there is no risk mitigation plan in place. Measures may include temporarily halting further recruitment. Any measure would be communicated to the relevant competent authority and IRB/EC.

## 11 QUALITY CONTROL AND QUALITY ASSURANCE

### 11.1 Periodic Monitoring

The study monitor will contact and visit the investigator periodically to review all study-related source data/records, verify the adherence to the protocol and the completeness, correctness and accuracy of all eCRF entries compared to source data. The investigator will co-operate with the study monitor to ensure that any discrepancies identified are resolved.

The study monitor must be given direct access to source documents (original documents, data and records). Direct access includes permission to examine, analyze, verify, and reproduce any records and reports that are important to the evaluation of the clinical study. Source data will be available for all data in the eCRFs, including all laboratory results.

### 11.2 Audit and Inspection

The investigator will make all study-related source data and records available to a qualified quality assurance auditor mandated by the Sponsor, or to IEC/IRB/regulatory inspectors, after reasonable notice. The main purposes of an audit or inspection are to confirm that the rights and welfare of the patients have been adequately protected, and that all data relevant for the assessment of safety and efficacy of the IMP have been reported to the Sponsor.

## 12 REPORTING AND PUBLICATION

### 12.1 Clinical Study Report

A CSR (in accordance with relevant guidelines and the Sponsor's SOPs) will be prepared by the Sponsor after completion of the study. The Co-ordinating investigator will approve the final study report after review.

### 12.2 Publication Policy

The results of this study may be published or presented at scientific meetings.

If this is envisaged by an investigator, the investigator agrees to inform the Sponsor and to submit all manuscripts or abstracts to the Sponsor prior to submission to an editorial board or scientific review committee. This will allow the Sponsor to protect proprietary information and to provide comments based on information that may not yet be available to the investigator.

In accordance with standard editorial and ethical practice, the Sponsor will support publication of multi-center studies only in their entirety and not as individual center data. Authorship will be determined by mutual agreement.

## 13 LIABILITIES AND INSURANCE

In order to cover any potential damage or injury occurring to a patient in association with the IMP or participation in the study, the Sponsor will contract insurance in accordance with local regulations.

The investigator is responsible for dispensing the IMP according to this protocol and for its secure storage and safe handling throughout the study.

Property of Octapharma. Do not copy or distribute without written permission.

## 15 APPENDICES

### 15.1 Blood Draw Guidelines

The latest EMA guideline (Ethical considerations for clinical trials on medicinal products conducted with minors, dated 18 September 2017) states that the blood sampling volume related to the clinical studies has to be minimized and justified. In general, blood loss should not exceed 3% of total blood volume (TBV) over 4 weeks and it should not exceed 1% of TBV at any single time [59].

The following table shows the acceptable blood volumes for different age ranges:

Body weight (kg)	Circulating total blood volume (mL)	Maximum allowable sample volume over 4 weeks (mL) - 3% of total blood volume	Maximum allowable sample volume at single time (mL) - 1% of total blood volume
12–20	960–1600	28.8–48.0	9.6–16.0
20–30	1600–2400	48.0–72.0	16.0–24.0
30–70	2400–5600	72.0–168.0	24.0–56.0

Maximum allowable research-related blood sample volumes. Total blood volume is approximately 80-90 ml/kg body weight. Of note: when routine health care requires significant blood sampling, these maximums may even be excessive

Expected blood volume collections for patients  $\geq 20$  kg will be maximum 16 mL at single time and 48 mL over four weeks. Expected blood volume collection  $<20$  kg will be maximum 12.8 mL at single time and 38.4 mL over four weeks. Following Exclusion Criterion 4 (Section 4.1.2) and the associated Centers for Disease Control and Prevention growth chart, no patients with body weight  $<16$  kg are expected to be enrolled in the study.

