#### **4.1.2 Exclusion Criteria**

Patients who meet any of the following criteria are not eligible for the study:

1. Onset of current PANS episode more than 12 months prior to first IMP treatment.
2. a. In patients with relapsing episodes: Onset of initial PANS episode more than 24 months prior to first IMP treatment  
b. In patients with relapsing episodes: Absence of significant improvement and stabilization between the episodes according to investigator's judgment.
3. Contraindications to receiving IVIG, including:
  - a. History of severe hypersensitivity, e.g. anaphylaxis or severe systemic response, to immunoglobulin, blood or plasma-derived products, or any component of Panzyga.
  - b. IgA deficiency with antibodies to IgA (<7 mg/dL).
  - c. Hyperviscosity syndromes or known or suspected hypercoagulable conditions as inferred from clinical history, which can increase risks of thrombosis associated with IVIG administration.
  - d. History of arterial or venous thrombotic or TEEs within the last year prior to Baseline. History of acquired or inherited thrombophilia any time prior to Baseline.
  - e. Need for live virus vaccine within three months after receiving study drug.
  - f. Renal dysfunction (creatinine > 120 µmol/L or 1.36 mg/dL), history of renal dysfunction, or known risk factor for renal dysfunction (chronic renal insufficiency, diabetes mellitus, taking known nephrotoxic medication). For Italy, estimated glomerular filtration rate (eGFR) needs to be calculated with the 2009 Schwartz equation (eGFR = k \* height/Serum creatinine (SCr), where k is 0.413) [2]. eGFR must not be below 30.

4. Severely restricted food intake likely to require parenteral nutrition, and <5th percentile BMI-for-age (BMI Percentile Calculator for Child and Teen based on Centers for Disease Control and Prevention growth charts for children and teens ages 2 through 19 years).
5. Body mass index  $\geq 40 \text{ kg/m}^2$ .
6. Presence of symptoms consistent with autism or schizophrenia, bipolar disorder, or other psychotic disorder (unless psychotic symptoms have onset coincident with PANS).
7. Presence of serious or unstable medical illness, psychiatric (e.g. high suicide risk) or behavioral symptoms that would make participation unsafe or study procedures too difficult to tolerate.
8. Treatment with systemic corticosteroids within eight weeks before randomization.
9. Treatment with NSAIDs within five days before randomization.

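### The fixed blood-sampling maxima for children under 20 kg meet the protocol's own 1% and 3% limits only from 16 kg upward, and Exclusion Criterion 4 does not supply that weight floor

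*Protocol*

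**What the plan says.** Protocol Section 15.1 (Blood Draw Guidelines) takes its limits from a European guideline on trials in minors: "blood loss should not exceed 3% of total blood volume (TBV) over 4 weeks and it should not exceed 1% of TBV at any single" occasion. A table gives the resulting volumes by body weight, starting at 12 kg, and a note adds that "Total blood volume is approximately 80-90 ml/kg body weight".

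The section then states the expected maximum collections in two weight bands. From 20 kg upward these are 16 mL at one time and 48 mL over four weeks. For patients under 20 the collection in "kg will be maximum 12.8 mL at single time and 38.4 mL over four weeks".

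The lower band is supported by one sentence: "Following Exclusion Criterion 4 (Section 4.1.2) and the associated Centers for Disease Control and Prevention growth chart, no patients with body weight" under 16 "kg are expected to be enrolled in the study".

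Exclusion Criterion 4 (Protocol Section 4.1.2, repeated in the Study Outline) reads: "Severely restricted food intake likely to require parenteral nutrition, and <5th percentile BMI-for-age", with a reference to the CDC percentile calculator. The only other body-size criterion visible is Criterion 5, an upper limit on BMI. Entry is open from 6 years of age.

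**The concern.** The lower-band maxima apply to every child under 20 kg, but they respect the 1% and 3% limits only if no such child weighs less than 16 kg. The one reason given for that floor is a criterion that does not mention weight. The visible text has no rule for a child who turns out lighter, although the section's own table runs down to 12 kg.

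What is at stake is a paediatric safety limit that the sponsor chose. The section says that sampling must be kept to a minimum and justified, and warns that even the tabulated maxima may be too much when routine care also needs blood. Endpoints and inference are not affected.

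**Working it through.** **Inputs.** All are from Protocol Section 15.1 unless stated.
- Limits: 1% of total blood volume (TBV) per draw, 3% over four weeks.
- TBV per kg: 80 in the table (960/12 = 1600/20 = 5600/70 = 80 mL/kg); 80 to 90 in the note.
- Maxima under 20 kg: 12.8 mL and 38.4 mL.
- Assumed lowest weight: 16 kg.
- BMI = weight / height² (SAP Section 8.4).

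**Step 1: reproduce the plan's figures.** Limit = fraction × TBV per kg × weight.
- At 16 kg: TBV = 80 × 16 = 1280 mL; 1% = 12.8 mL; 3% = 38.4 mL. This matches exactly.
- At 20 kg: TBV = 1600 mL; 1% = 16 mL; 3% = 48 mL. This matches the upper-band maxima.

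Each band is therefore set at its assumed lowest weight, and the lower band is safe only if 16 kg really is the lowest.

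**Step 2: break-even weight.** Weight = 12.8 / (0.01 × TBV per kg). The four-week limit gives the same answer, since 38.4 = 3 × 12.8.
- 80 mL/kg: 16.0 kg
- 85 mL/kg: 15.1 kg
- 90 mL/kg: 14.2 kg

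**Step 3: share of TBV if the full maximum is drawn.** Share = 12.8 / (TBV per kg × weight) per draw, and 38.4 / (TBV per kg × weight) over four weeks.

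| Weight | At 80 mL/kg | At 90 mL/kg |
|---|---|---|
| 16 kg | 1.00% / 3.00% | 0.89% / 2.67% |
| 15 kg | 1.07% / 3.20% | 0.95% / 2.84% |
| 14 kg | 1.14% / 3.43% | 1.02% / 3.05% |
| 12 kg | 1.33% / 4.00% | 1.19% / 3.56% |

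At 12 kg the table's own limits are 9.6 and 28.8 mL, so the fixed maxima are 3.2 and 9.6 mL higher (12.8/9.6 = 38.4/28.8 = 1.33).

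**Step 4: does Criterion 4 give a 16 kg floor?** Its wording can be read in two ways.
- *Both conditions are needed.* A child below the 5th BMI percentile who is not likely to need parenteral nutrition stays eligible, whatever the weight.
- *Either condition excludes.* Every child below the 5th percentile is then out, but BMI still does not bound weight, because a short child can have an acceptable BMI at a low weight.

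The documents give no chart values. As an assumption for illustration, take a BMI of 13 to 15 kg/m² at age 6. A weight of 16 kg then corresponds to a height of √(16/13) = 1.109 m down to √(16/15) = 1.033 m, and a shorter child at the same BMI weighs less. For example, BMI 14 at 1.04 m gives 14 × 1.0816 = 15.1 kg.

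Criterion 4 yields no weight floor on either reading. It is also an entry criterion, while participation lasts 18 weeks (Protocol Section 6.2.1), so weight can fall afterwards.

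**The case against.** The strongest reply is that no limit is shown to be broken. The volumes are stated as maxima of expected collections. What is drawn at each visit lies in redacted text (Section 6.1, the laboratory sections and both flow charts), so neither the real volumes nor a possible low-weight rule can be seen. This stands: a reader might infer that light children will be over-sampled, and the documents do not support that.

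Second, the table uses the low end of the stated TBV range. This also stands in part. At 90 mL/kg a 15 kg child is within both limits, and only children below about 14.2 kg exceed them. But 80 mL/kg is the basis on which the protocol computed its own limits.

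Third, Section 15.1 speaks of an expectation, not a guarantee, and words the limits as general guidance. That is fair, but the expectation is attributed to a criterion that cannot produce it, and nothing visible covers the case where it fails. The table's 12 kg starting point is only a general weight band and does not show that such children will enrol.

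Fourth, a reader might add that food restriction is to be expected in PANS, which would make light children common. It is not among the seven symptom categories in Inclusion Criterion 2; the visible text raises it only in Criterion 4, as part of an exclusion.

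Finally, this is not a calculation error: every figure in Section 15.1 reproduces.

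**Conclusion.** The point holds as an internal inconsistency. The maxima for patients under 20 kg equal the protocol's own limits at 16 kg on the table's basis (about 14.2 kg at 90 mL/kg), and the cited criterion does not keep lighter children out. If the full maximum were drawn, the excess would be small at 15 kg (1.07% and 3.2% at 80 mL/kg; none at 90 mL/kg). It would reach a third above the table's limits at 12 kg on the 80 mL/kg basis.

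The conclusion rests on the visible eligibility criteria being complete as to body size and on full use of the stated maxima. It does not rest on how the wording of Criterion 4 is read. The number of children concerned cannot be computed from the documents and is likely to be small. The matter deserves correction because it concerns a paediatric safety limit and is cheap to put right, not because harm has been shown.

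**What to change.** Reconcile Section 15.1 with Criterion 4:

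1. Keep 12.8 mL and 38.4 mL as ceilings, and state that for any patient under 20 kg the permitted volume is the lower of the fixed ceiling and the protocol's own 1% and 3% limits at the table's 80 mL/kg for current weight. That is min(12.8, 0.8 × weight) mL per draw and min(38.4, 2.4 × weight) mL over four weeks: for example 12.0 and 36.0 mL at 15 kg, and 9.6 and 28.8 mL at 12 kg.
2. Apply this at Screening too. Section 5.4 has weight measured before each infusion cycle, which does not cover the Screening draw, and Screening can fall in the same four-week window as Baseline.
3. Remove the statement that rests the 16 kg floor on Criterion 4.

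The lower-of rule is needed because a pure per-kg limit would raise the permitted volume for children between 16 and 20 kg. At 18 kg it would allow 14.4 and 43.2 mL in place of 12.8 and 38.4 mL.

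If volume has to be cut, the biomarker sample (Section 7.4.2), taken only with consent, is the one the documents show to be optional. The stored serum samples should not be treated as optional, since Section 7.5 requires them from each patient. Section 10.3 mentions an optional collection for central storage without saying which sample it means; the sponsor should make that clear.

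The cost is a short change to the appendix and the laboratory instructions, and an occasional biomarker sample lost in the lightest children.

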## 15.2 Flow Chart of Assessments for Europe

1. [REDACTED]

2. [REDACTED]

3. [REDACTED]
4. [REDACTED]
5. [REDACTED]
6. [REDACTED]
7. [REDACTED]
8. [REDACTED]
9. [REDACTED]
10. [REDACTED]
11. [REDACTED]
12. [REDACTED]
13. [REDACTED]
14. [REDACTED]

Property of Octapharma. Do not copy or distribute without permission.

Final 3.0	26-Jan-2021	[REDACTED]	Adjust wording to reflect revised eligibility criteria, unified use of term patient rather than subject, safety review of first 6 patients added, collection of non treatment-emergent AEs, introduction of the MINI-KID assessment, specific biomarker panel (autoimmune encephalopathy) replaced by backup blood sample for later analysis
Final 4.0	28-Jul-2021	[REDACTED]	Update based on Protocol Version 4.0: correct the number of items in SNAP-IV Scale; Correct the item score in CY-BOCS; Clarify the significance level for the interim analysis; Adjust wording in sample size estimation; Add covariates for multiple imputation.
Final 5.0	21-Jul-2023	[REDACTED]	Update based on Protocol Version 5.0 and 6.0: Add correlation analysis between CYBOCS and CGI-I. Add exploratory analysis for the percentage of patients with PANS improvement. Add interim review after 20 patients have completed blinded treatment.

Property of Octapharma. Do not copy or distribute without permission.

Abbreviations

ADHD	Attention-Deficit Hyperactivity Disorder	HTR	Hemolytic Transfusion Reaction
AE	Adverse Event	ICH	International Conference on Harmonization
ATC	Anatomical Therapeutic Chemical	IDMC	Independent Data Monitoring Committee
BMI	Body Mass Index	ITT	Intention-To-Treat
BW	Bodyweight	IVIG	Intravenous Immunoglobulin
CD	Conduct Disorder	MAR	Missing at Random
CGI	Clinical Global Impression	MedDRA	Medical Dictionary for Regulatory Activities
CGI-I	Clinical Global Impression - Improvement	MINI-KID	Mini International Neuropsychiatric Interview for Children and Adolescents
CGI-S	Clinical Global Impression – Severity	OC	Obsessive–Compulsive
CI	Confidence Interval	ODD	Oppositional Defiant Disorder
COIS	Parent & Child OC Impact Scale – Revised	PANDAS	Pediatric Autoimmune Neuropsychiatric Disorders Associated with Streptococcal infection
COIS-RC	Child Obsessive-compulsive Impact Scale - Revised – Child	PANS	Patients with Acute-onset Neuropsychiatric Syndrome
COIS-RP	Child Obsessive-compulsive Impact Scale - Revised – Parent	PP	Per Protocol
CSR	Clinical Study Report	PTQ	Parent Tic Questionnaire
C-SSRS	Columbia Suicide Severity Rating Scale	SAE	Serious Adverse Event
CY-BOCS	Children's Yale-Brown Obsessive Compulsive Scale	SAP	Statistical Analysis Plan
DB	Database	SNAP-IV	Swanson, Nolan, and Pelham Rating Scale
DSM	American Psychiatric Association's Diagnostic and Statistical Manual	SSRI	Selective Serotonin Reuptake Inhibitors

The purpose of this Statistical Analysis Plan (SAP) is to describe the statistical methods to be deployed for the collection and analysis of data for the study with protocol number NGAM-13. The SAP will be finalized prior to database lock and any statistical analysis. Any deviations from the SAP after database lock will be documented in the final Clinical Study Report (CSR).

This phase 3 study is conducted in pediatric patients with acute-onset neuropsychiatric syndrome (PANS) to confirm that Panzyga is superior to placebo (saline solution) in reducing severity of symptoms associated with PANS in this patient group. It is designed as a prospective, multicenter, randomized, double-blind, parallel group, placebo-controlled, Phase 3 superiority study, with an additional double-blind, crossover safety and efficacy follow-up phase.

Efficacy will be evaluated by comparison of the observed changes in neuropsychiatric symptomatology and behavior, determined by the Children's Yale-Brown Obsessive Compulsive Scale (CY-BOCS), between the randomized treatment groups:

- Panzyga (Immune Globulin Intravenous, Human 10%)
- Placebo (saline solution)

In addition to this primary endpoint, secondary efficacy and exploratory evaluations will cover the durability of the clinical benefit, and behavioral changes by means of the following standardized assessments: Clinical Global Impression (CGI), Parent & Child QC Impact Scale – Revised (COIS-RP and COIS-RC), Swanson, Nolan, and Pelham Rating Scale (SNAP-IV, 26 item), Parent Tic Questionnaire (PTQ).

Furthermore safety assessments (adverse events, vital signs, physical examinations, laboratory parameters) will be performed throughout the study period, and the pharmacokinetics of Panzyga in PANS patients will be investigated. A blood sample will be collected at Screening and Week 18/Early Termination Visit for later analyses (assessments to be determined).

Because the available knowledge on the effect of intravenous immunoglobulin (IVIG) in the PANS population is limited, this study will deploy an adaptive enrichment design with an interim analysis after █ patients have completed the initial 9-week treatment period, at which time a decision will be made based on prespecified criteria whether to continue enrollment in the overall population (PANS) or to restrict future enrollment on a targeted subpopulation, including e.g. the subgroup of patients diagnosed with pediatric autoimmune neuropsychiatric disorders associated with streptococcal infection (PANDAS); please refer to section 5.1 for details on the interim analysis.

The possible design adaptations at the interim analysis will also include a sample size re-assessment on basis of the observed changes in CY-BOCS.

The structure and content of this SAP provides sufficient detail to meet the requirements identified by the FDA and International Conference on Harmonization (ICH) of Technical Requirements for Registration of Pharmaceuticals for Human Use: Guidance on Statistical Principles in Clinical Trials¹.

The following documents were reviewed in preparation of this SAP:

- Clinical Study Protocol NGAM-13, Version 3.0, dated 25-Jan-2021

¹ International Conference on Harmonization. (1998). Guidance on Statistical Principles. ICH Topic E9 (Statistical Principles for Clinical Trials), and its Addendum on Estimands and Sensitivity Analysis, E9(R1), 2019-11-20.

The reader of this SAP is encouraged to also read the clinical protocol for details on the planned conduct of this study. Operational aspects related to collection and timing of planned clinical assessments are not repeated in this SAP unless relevant for the specification of the planned analyses.

Property of Octapharma. Do not copy or distribute without written permission.

2. Purpose

This SAP outlines the statistical analyses to be performed on data collected in study NGAM-13, and the resulting output that will be compiled to support the completion of the CSR.

The planned analyses identified in this SAP will be included in regulatory submissions and/or future manuscripts. Exploratory analyses not necessarily identified in this SAP may be performed to support the clinical development program. Any post-hoc or unplanned analyses performed that are not identified in the final SAP will be clearly identified in the respective CSR.

The statistical output provided to the medical writer of the CSR will closely follow the ICH guideline for industry on topic E3 (Structure and Content of Clinical Study Reports²) to facilitate the subsequent compilation of the CSR.

This statistical output will consist of tables, figures, and listings, including

- Tables, figures, and listings used or referenced in, or appended to the CSR as detailed in the remainder of this SAP (section 14 of the CSR)
 - Demographic data summary figures and tables
 - Efficacy data summary figures and tables
 - Safety data summary figures and tables
- Listings provided as appendices to the CSR
 - Patient data listings (section 16.2 of the CSR)
 - Individual patient data listings (section 16.4 of the CSR) will be covered by inclusion of SAS datasets into the electronic submissions to the authorities

A detailed list of all tables, figures and listings will be supplied in a separate document later when all feedback from authorities will be available.

If relevant aspects of the study design are adapted following the interim analysis, this SAP will be updated accordingly.

² International Conference on Harmonization. (1996). Structure and Content of Clinical Study Reports. Structure and Content of Clinical Study Reports (Guideline for Industry) (S. 37). London: International Conference on Harmonization.

3. Study Objectives and Endpoints

